## 5.0 TREATMENT PLAN

## 5.1 Treatment Dosage and Administration

One hundred and thirty participants with liver cirrhosis and an initial HCC diagnosis will be randomized into one of 2 groups: 65 participants will be randomized to receive 40 mg pravastatin per day and 65 participants will be randomized to receive a placebo identical in color, consistency, and appearance to pravastatin 40 mg. Pravastatin and placebo will be provided as over-encapsulated tablets. Dosing will extend for 12 months

- Agent(s): Pravastatin and placebo
- Daily dose(s) and regimen(s) for each agent: One capsule per day
- Duration for each agent: Daily treatment for 12 months

The usual recommended dose of pravastatin is 10-40 mg/day, and the toxicity and tolerability are comparable for 20 mg and 40 mg (21-23). In a prior published trial of patients with chronic hepatitis or cirrhosis and HCC, pravastatin dosing began at 20 mg and was titrated up to 40 mg, and no serious side effects or discontinuation of therapy were noted (37). Thus, we feel that a 40 mg dose will be well-tolerated by the participants in this trial.

Patients will self-administer the 40 mg capsule of pravastatin or placebo daily in the evening. Patients will be instructed to take the study agent at bedtime or with an evening meal. Each participant will be given one bottle of 120 capsules at Study Visit 1 (90-day supply + buffer) and one bottle of 120 capsules (90-day supply + buffer) at Study Visit 3 (Month 3), Study Visit 4 (Month 6), and Study Visit 5 (Month 9).

## 5.2 Method of Assigning Subjects to Treatment Groups

A designee of the QMC at Cedars-Sinai will conduct a final eligibility check prior to registration. Randomization will be carried out by the Research Pharmacy at each site among consented subjects who meet all eligibility criteria after the eligibility evaluations.

#### 5.3 Blinding/Unblinding

Due to the objectives of the study, the identity of test and control treatments will not be known to investigators, research staff, or subjects. The following study procedures will be in place to ensure double-blind administration of study treatments.

- The study biostatisticians will set up randomization blocks.
- After registration, participants will be randomized to treatment with the study agent or placebo
- Investigators and participants will be blinded as to the result of randomization. The following people will be unblinded: the study biostatisticians at Cedars-Sinai and the investigational pharmacists at each participating site.
- The investigational pharmacist will manage the study agent and placebo.
- Unblinding will only occur when it is deemed medically necessary.

## 5.3.1 Emergency Unblinding

• Emergency unblindings are left up to the discretion of the accrual site clinical PI.

- Prior to unblinding, the accrual site should attempt to notify the protocol PI that an unblinding will occur, and why.
- The accrual site should work with their pharmacy in the event of an emergency that requires an immediate unblinding.
- In case of medical emergency, the participant may discontinue the study agent under the advice of a doctor, and if unblinding is deemed medically necessary by the accrual site clinical investigator, this can be addressed during the next business hours.

## 5.3.2 Non-Emergency Unblinding

- The pharmacy may unblind in a non-emergency only upon approval of the protocol PI.
- In the event of a non-emergency unblinding, the pharmacy will receive an Unblinding Request Note to File indicating:
  - The PID(s) to be unblinded
  - The reason for unblinding
  - Study staff responsible for unblinding
  - Signed or emailed approval by the protocol PI
- Upon receipt, the pharmacy will compose a Pharmacy Note to File based on their dispensing records, indicating:
  - The requested PID(s)
  - The corresponding unblinded treatment assignments
  - A pharmacist signature
- The Pharmacy Note to File should be sent to the accrual site clinical investigator.
- Once a participant is unblinded, they will be taken off treatment but may remain on study as long as no off study criteria are met.

## 5.4 Toxicities and Dosing Delays/Dose Modifications

## Toxicities

All participants will be evaluable for toxicity from the time of their first dose of pravastatin.

## 5.5 Concomitant Medications/Treatments

All medications (prescription and over-the-counter), vitamin and mineral supplements, and/or herbs taken by the participant will be documented on the concomitant medication CRF and will include: 1) start and stop date, 2) dose, 3) frequency, 4) route of administration, and 5) indication. Medications taken for a procedure (*e.g.*, biopsy) should also be included.

Patients are advised not to consume any form of grapefruit (e.g., juice, fruit, grapefruit seed extract, dietary supplements containing grapefruit) while on pravastatin as grapefruit may increase the blood levels of pravastatin. Participants enrolled in the study will be instructed to avoid all forms of grapefruit.

The combined use of pravastatin with systemic formulations of gemfibrozil, cyclosporine, clarithromycin, erythromycin, azithromycin, colchicine, fibrates, and niacins contraindicated due to an increased risk for myopathy. Additionally, other drug-drug interactions exist with pravastatin such as; boceprevir, cimetidine, cholestyramine, colestipol, darunavir, digoxin, diltiazem, fluconazole, itraconazole, probucol, ritonavir, verapamil, and warfarin. These medications should be avoided if possible or used with caution per investigator discretion.

Pravastatin must be administered either 1 hour or more before or at least 4 hours after bile acid resins (e.g., cholestyramine, colestipol). Patients will be screened for contraindications to pravastatin prior to enrollment in the study. Patients with known active infection with HIV will be excluded from the study. Patients will be advised not to use contraindicated medications during the study and will be excluded if systemic use of any contraindicated medication is unavoidable. Concomitant medications will be reviewed at study visits and during follow-up telephone calls. Participants will be closely monitored for symptoms and side effects to the study drug and will be instructed to call the study doctor immediately if they have a serious adverse reaction.

## 5.6 Adherence/Compliance

Compliance will be measured by pill counts and patient diaries. Compliance is defined as 85% of the total dose of the study agent. A participant diary will be used to monitor daily compliance. Participants will be instructed to record the time the study drug was taken each day in the diary, as well as any potential side effects. Diaries will be reviewed and compliance will be assessed at Study Visits 2-6. Compliance will be reinforced throughout the study with regular telephone calls and text/email messages as detailed in Section 6.2.1.

Patients will return the unused capsules to the study coordinator at Visits 3 through 6. Study agent should be received and accounted for according to local institutional policy. See Pharmacy Manual for further details on study agent accountability and compliance. All participants that receive a study agent for any period of time will be evaluable for toxicity.

## 5.7 Stopping Rules

Continuous assessment of the 40 mg dose of pravastatin will be ongoing to ensure safety and toxicity monitoring at this dose. Accrual will be stopped if 30% or more of study participants come off the study agent due to serious adverse events probably or definitely related to the agent, after at least 15 patients have been registered. Toxicity will be reviewed to determine whether accrual to the study should be permanently stopped.

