## 3.0 STUDY DESIGN SUMMARY

This is a Phase II randomized, double-blinded, placebo-controlled clinical trial including 130 patients with cirrhosis diagnosed with HCC recruited from Cedars-Sinai Medical Center (CSMC), Ronald Reagan UCLA Medical Center (UCLA), Northwestern Memorial Hospital (NWU), UCSF Medical Center (UCSF), or Emory University Woodruff Health Sciences Center (EU). We will randomize study participants 1:1 to daily pravastatin 40 mg or placebo, created to be identical in color, consistency, and appearance to pravastatin, for an intervention period of 12 months. We expect to have a final sample of 47 study participants on pravastatin and 47 on placebo after accounting for the competing risk of transplantation or death due to cirrhosis (Figure 3). Evaluations will be taken at baseline and at study visits 1-6. Screening data will be reviewed to determine subject eligibility. Subjects who meet all inclusion criteria and none of the exclusion criteria will be enrolled in the study.

The following treatment regimens will be used:

- Experimental treatment: 40 mg pravastatin (N=65).
- Placebo: (N=65).

Total duration of active participation will be 12 months. Total duration of the study is expected to be 5 years.

[figure not shown]

Figure 3. Study profile for the primary endpoint of time to HCC recurrence

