## 5.8 Duration of Therapy

Participants will be on study agent pravastatin or placebo for a duration of 12 months.

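### The Section 5.7 toxicity rule is meant to watch pravastatin 40 mg but counts both arms, so placebo patients dilute its 30% trigger by up to two-fold

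*Combined protocol and SAP*

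**What the plan says.** Section 5.7 opens with its purpose: "Continuous assessment of the 40 mg dose of pravastatin will be ongoing to ensure safety and toxicity monitoring at this dose". The trigger follows: "Accrual will be stopped if 30% or more of study participants come off the study agent due to serious adverse events". The events that count are "serious adverse events probably or definitely related to the agent", and the rule takes effect "after at least 15 patients have been registered". When it fires, toxicity is reviewed to decide whether accrual stops for good. No derivation or operating characteristics are given.

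The terms in the rule are not confined to one arm. Section 3.0 uses *study participants* for everyone randomized: "We will randomize study participants 1:1 to daily pravastatin 40 mg or placebo". *Study agent* has two meanings. Section 5.8 applies it to both arms: "Participants will be on study agent pravastatin or placebo for a duration of 12 months". Section 5.3 sets it against placebo: "After registration, participants will be randomized to treatment with the study agent or placebo".

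On who could compute a percentage by arm, Section 5.3 states: "The following people will be unblinded: the study biostatisticians at Cedars-Sinai", together with the site pharmacists. Section 10.3.2 says the same. Section 10.5.2 describes DSMC reviews of SAEs but does not mention review by arm.

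**The concern.** The rule's purpose concerns one arm and its percentage concerns two. If few placebo patients stop treatment for an SAE judged probably or definitely related, the placebo arm adds to the denominator and almost nothing to the numerator. The pooled percentage is then about half the pravastatin rate.

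Reading *study agent* as pravastatin only, as Section 5.3 does, does not remove the problem. It restricts the numerator to pravastatin patients and leaves all participants in the denominator.

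This matters because Section 5.7 holds the only numerical trigger that stops accrual for the whole trial, and Section 9.3.3 plans no interim analysis. Section 1.2 acknowledges that underlying liver disease is a label-defined contraindication, and every participant has cirrhosis. A pravastatin toxicity rate that a reader of Section 5.7 would expect to halt accrual may well not do so.

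**Working it through.** The plan gives a threshold and no derived figure, so there is nothing to reproduce first.

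**Inputs from the documents.** Threshold 30% or more, starting at 15 registered (Section 5.7). Allocation 1:1 (Sections 3.0 and 9.1). 130 randomized, 65 per arm (Section 9.2).

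**Assumptions.** Counted placebo rate 0%, 5% or 10%. For the simulations: permuted blocks of 4, outcomes known immediately, and the rule checked after every patient from 15 to 130.

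**Step 1: the pravastatin rate that corresponds to the trigger.** With equal arms, pooled rate = (pravastatin rate + placebo rate) / 2. Setting this to 0.30 gives pravastatin rate = 0.60 − placebo rate:

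- placebo 0%: 60%
- placebo 5%: 55%
- placebo 10%: 50%

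In counts, 0.30 × 130 = 39 patients. With no placebo events that is 39/65 = 60% of the pravastatin arm. At the first look, 0.30 × 15 = 4.5, so 5 patients are needed: 5/8 = 62.5% or 5/7 = 71% of those on pravastatin.

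**Step 2: the chance of firing at the first look.** Take 8 of the first 15 on pravastatin, a true pravastatin rate of 30% and no placebo events. The binomial probability of at least 5 of 8 is 5.8%. For the same 30% counted within the arm, 0.30 × 8 = 2.4, so 3 are needed, and the probability of at least 3 of 8 is 44.8%.

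**Step 3: the chance of firing at any look** (20,000 simulated trials per setting; the by-arm count also starts at 15 registered in total):

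| True pravastatin rate | Assumed placebo rate | Pooled count | Pravastatin arm only |
|---|---|---|---|
| 30% | 0% | about 8% | about 86% |
| 30% | 5% | about 17% | about 86% |
| 30% | 10% | about 30% | about 86% |
| 40% | 0% | about 25% | about 99% |
| 50% | 0% | about 57% | about 100% |

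With no placebo events, pooled firing reaches even odds near a true pravastatin rate of 48%. This is below the 60% of Step 1 because repeated looks at small numbers can trigger the rule by chance.

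**Step 4: what a by-arm count costs at lower rates.** With the 30% figure and the start at 15 registered both unchanged, it fires about 1%, 8%, 22% and 43% of the time at true pravastatin rates of 5%, 10%, 15% and 20%. The cause is the early start: with 7 or 8 patients on pravastatin, 3 events suffice.

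**The case against.** **Other safeguards exist.** A reader might infer that the trial has no working safety stop. The documents do not support that. Section 5.4 sets patient-level discontinuation criteria. Section 7.7.1 sends related SAEs to the DSMC within 24 hours for ad hoc review, and Section 10.5.2 has the DSMC reviewing SAEs at its meetings. What stands is narrower: none of these is a numerical trigger for accrual, and the DSMC is required to meet only once a year.

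**60% is not the rate at which firing becomes likely.** It is tempting to say that 60% of pravastatin patients must fail before the rule can be expected to fire. With a check after every patient, firing is already more likely than not at a true 50%. The 60% figure is the observed rate that corresponds to the trigger when no placebo event counts.

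**Placebo events may count.** Attribution is made by blinded staff, so some placebo events could be judged related. This is correct, and it is why a range is shown. At an assumed 10% on placebo the pooled rule still fires about 30% of the time, against about 86% by arm.

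**A pooled trigger protects the blind and may be deliberate.** Section 5.7 names 30% of participants; it does not say that 30% on pravastatin is the target. By-arm review might also already happen: Section 7.5 makes treatment assignment code a required adverse event field, and the DSMC Charter is not part of these documents. These points stand as reasons not to assume an intended pravastatin rate. They do not reconcile the rule's wording with its stated purpose, and the blind can be kept because unblinded biostatisticians are already in place.

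**The simulations check after every patient.** If the percentage were looked at only at DSMC meetings, the by-arm advantage would be smaller. With three illustrative looks at 43, 87 and 130 patients, by-arm firing at a true 30% falls to about 67%. Section 5.7, however, describes continuous assessment. Delayed outcomes work against the pooled rule, because recently registered patients with little exposure enter the denominator.

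**Conclusion.** The point holds as a mismatch between purpose and denominator. Counted as written, the rule is diluted up to two-fold by the placebo arm: a pooled 30% corresponds to 50% to 60% on pravastatin for assumed placebo rates of 10% down to 0%. At a true pravastatin rate of 30% it fires about 8% to 30% of the time over that range, against about 86% for the same percentage counted by arm.

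The two-fold dilution follows from 1:1 allocation alone. The firing probabilities also depend on the assumed placebo rates, blocks of 4, immediate outcomes and a check after every patient. The inconsistent use of *study agent* adds doubt about the numerator but cannot repair the denominator. The conclusion concerns the one numerical accrual trigger in the plan, not patient safety oversight as a whole.

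**What to change.** - State in Section 5.7 which arm or arms form the numerator and the denominator so that both match the stated purpose, and reconcile the use of *study agent* between Sections 5.3 and 5.8.
- Have the already unblinded biostatistician compute the percentage by arm on the rule's continuous schedule and give it confidentially to the DSMC. Investigators, site staff and participants stay blinded.
- State the rule's operating characteristics over a range of true rates in each arm.
- Leave the threshold and starting count to the sponsor and DSMC, who should see the Step 4 figures before deciding whether to carry the present values over to a by-arm count.

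The cost is a protocol wording change, a short simulation and a recurring tabulation by staff already unblinded. There are two downsides: the DSMC sees safety counts by arm, and with the present figures a by-arm count would fire about 22% and 43% of the time at true pravastatin rates of 15% and 20%.

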## 5.8 Duration of Therapy

Participants will be on study agent pravastatin or placebo for a duration of 12 months.

## 5.9 Duration of Follow Up

Clinical research staff will make follow-up telephone calls to study participants on days 30  $\pm$  7, 60  $\pm$  7, and 90  $\pm$  7 after completion of Study Visit 6 to assess symptoms and adverse events. For all patients who enter the trial and receive a liver transplant before the end of this 5-year study (within or beyond the 12-month intervention period), we will obtain specimens at the time of transplantation.

## 5.10 Removal of Patients from Protocol

Patients will be removed from the study when any of the criteria listed in Section 6.7 apply. Notify the Principal Investigator, and document the reason for study removal and the date the patient was removed in the Case Report Form. The patient should be followed-up per protocol (Section 6.3).

## 5.11 Subject Replacement

Subjects who withdraw from the study treatment will not be replaced.

#### 6.0 STUDY PROCEDURES

#### 6.1 Screening/Baseline Procedures

Assessments performed exclusively to determine eligibility for this study will be done only after obtaining informed consent. Assessments performed for clinical indications (not exclusively to determine study eligibility) may be used for baseline values even if the studies were done before informed consent was obtained. If a patient's lab results in the medical record do not meet the eligibility criteria, the patient may still be considered potentially eligible because blood tests may be done at the Screening visit. The study coordinator will collect a urine sample to test for pregnancy (for women of child bearing potential, defined in 3.1.2), and blood tests will be conducted for confirmation of eligibility (see section 4.0 for details). MedQIA will review the patient's scans to confirm eligibility per the *Imaging Charter* (see 4.1.3 and 4.1.4).

All screening procedures must be performed within 60 days prior to registration with the exception of imaging. Historical (standard of care) images taken greater than 30 days prior to registration will be required to verify eligibility per the *Imaging Charter*. The screening procedures are detailed below.

# 6.1.1 Screening Visit- Consent, Final determination of eligibility, registration, and randomization

After consent has been obtained, a final assessment of eligibility will be conducted. Consented patients will undergo additional screening and testing at the clinic to confirm eligibility and safety of study drug initiation.

For definition of any procedures, please see section 3.1 Study Measurements. The following procedures will be performed during the Screening Visit:

- Physical assessment
- Pregnancy test
- Imaging review
- Eligibility blood specimen
  - o AFP
  - o Blood chemistry
  - PT/INR
- Review Subject Eligibility Criteria

• All inclusion and exclusion criteria will be evaluated for the patient

- Registration and randomization
  - Eligible participants will be registered and randomized to pravastatin or placebo

## 6.2 **Procedures During Treatment**

There will be six study visits along with telephone calls during treatment. A packet of material, including an appointment letter, a map, and parking instructions will be sent to the study participant prior to each scheduled study visit. For definition of any items please see section 3.1 Study Measurements.

## 6.2.1 Telephone Calls and Email/Text Messages.

Study participants will be followed during the intervention via telephone calls once a month ( $\pm$  3 days) by the clinical research staff to assess compliance and adverse events. In addition, participants will receive a phone call the day before each scheduled study visit to remind them to bring any leftover study drugs and the study diary with them to the visit.

The following information with be collected during the telephone calls:

- Medication compliance review
- Concomitant medications review
- Symptom/adverse event assessment

#### 6.2.2 Study Visit 1- Baseline Testing and Initiation of the Intervention

Study Visit 1 (Baseline measurements) will occur 0-30 days after the Screening Visit. The following procedures will be performed during this visit:

- Medical history
- Concomitant medication review
- Health assessment
- Clinical blood specimen
  - Blood chemistry
    - o Lipid
    - HbA1C
  - CPK
  - Research blood specimen
- Liver stiffness
- Liver fat fraction
- Baseline risk factor questionnaire

- Baseline symptom assessment
- Study agent
  - Dispense the study agent (one bottle of 120 capsules) and review instructions for how to take it
  - Dispense and review the study diary

## 6.2.3 Study Visit 2

Study Visit 2 will occur 1 month (± 15 days) after initiation of the Intervention. The following procedures will be performed during this visit:

- Symptom/adverse events assessment
- Medical history
- Concomitant medications review
- Health assessment
- Clinical blood specimen
  - Blood chemistry
  - o Lipid
- Imaging review
- Study agent
  - Collect study agent and diary
  - Assess compliance (pill count)
  - Review study diary
  - Dispense study agent (same bottle that was brought to the visit/collected for pill count)

## 6.2.4 Study Visit 3

Study Visit 3 will occur 3 months ( $\pm$  15 days) after initiation of the intervention (study drug initiation).

The following procedures will be performed during this visit:

- Symptom/adverse events assessment
- Medical history
- Concomitant medications review
- Health assessment
- Imaging review
- Study agent
  - Collect study agent and diary
  - Assess compliance (pill count)
  - Review study diary
  - o Dispense study agent (one new bottle of 120 capsules) and diary

## 6.2.5 Study Visit 4

Study Visit 4 will occur 6 months ( $\pm$  15 days) after initiation of the Intervention (study drug initiation). The following procedures will be performed during this visit:

- Symptom/adverse events assessment
- Medical history
- Concomitant medications review
- Physical assessment
- Clinical blood specimen
  - Blood chemistry
  - o Hba1c
  - $\circ$  AFP
- Research blood specimen
- Follow-up risk factor questionnaire

- Imaging review
- Study agent
  - Collect study agent and diary
  - Assess compliance (pill count)
  - Review study diary
  - Dispense study agent (one bottle of 120 capsules) and diary

## 6.2.6 Study Visit 5

Study Visit 5 will occur 9 months ( $\pm$  15 days) after initiation of the intervention (study drug initiation). The following procedures will be performed during this visit:

- Symptom/adverse events assessment
- Medical history
- Concomitant medications review
- Health assessment
- Imaging review
- Study Agent
  - Collect study agent and diary
  - Assess compliance (pill count)
  - Review study diary
  - o Dispense study agent (one new bottle of 120 capsules) and diary

## 6.2.7 Study Visit 6

Study Visit 6 will occur 12 months ( $\pm$  15 days) after initiation of the intervention (study drug initiation). The following procedures will be performed during this visit:

- Symptom/adverse events assessment
- Medical history
- Concomitant medication review
- Physical assessment
- Clinical blood specimen
  - Blood Chemistry
    - o Lipid
    - o Hba1c
    - o PT/INR
    - o AFP
- Research blood specimen
- Imaging review
- Liver stiffness
- Liver fat fraction
- Follow-up risk factor questionnaire
- Study agent
  - Collect study agent and diary
  - Assess compliance (pill count)
  - Review study diary

**6.2.8** Unscheduled Visit (Transplant Specimen Collection). For all patients who enter the trial and receive a liver transplant before the end of this study, we will obtain specimens at the time of transplantation. The research blood specimen will be collected prior to transplant (while the patient is being prepped for surgery).

- Research blood specimen
- Transplant tissue specimen

